8.2.2 SGA

Subjects will complete a global assessment of their RA disease activity using the subject's global assessment of disease activity (SGA) item, a numerical rating scale (NRS) from "0" (inactive) to "10" (very active).

No imputations for missing data will be done.

8.2.3 Subject's Pain Assessment

Subjects will assess the severity of their current RA-related pain using a NRS from "0" (no pain) to "10" (worst pain imaginable).

No imputations for missing data will be done.

8.2.4 EGA

The joint evaluator will complete the evaluator's global assessment of disease activity item (EGA) using a NRS from "0" (inactive) to "10" (very active).

No imputations for missing data will be done.

8.2.5 HAQ-DI

The functional status of the subject will be assessed by means of the Health Assessment Questionnaire Disability Index (HAQ-DI). This 20-question instrument assesses the degree of difficulty a person has in accomplishing tasks in 8 functional areas:

- Dressing and grooming
- Arising
- Eating
- Walking
- Hygiene
- Reach
- Grip
- Common daily activities

Each functional area contains at least 2 questions. For each question, there is a 4-level response set that is scored from 0 (without any difficulty) to 3 (unable to do). If aids or devices or physical assistance are used for a specific functional area (**Table 6**), and the maximum response of this functional area is 0 or 1, the according value is increased to a score of 2.

Table 6: HAQ-DI Category Scores Depending on Aids, Devices or Physical Assistance

Aid or Equipment	Will be Associated with Category Score
Walking stick/frame, crutches, wheelchair	Walking
Aids used for dressing	Dressing and grooming
Specially adapted utensils	Eating
Specially adapted chair	Rising
Raised toilet seat, bath rail, bath seat	Hygiene
Long-handled appliance in bathroom	Hygiene
Long-handled appliance for reaching	Reach
Jar opener	Grip
Other (1)	Dressing & grooming, rising, eating, walking
Other (2)	hygiene, reach, grip, common daily activities

If “other” is marked as an aid or equipment, then this can be assigned to a group of four functional areas and will be handled as an aid or equipment for each of the four functional areas. Therefore,

if the maximum score of a functional area is 0 or 1, that value is increased to a score of 2 for each of the four functional areas.

Regarding these corrections, the highest response within each functional area determines the score of that specific functional area. If no questions within a given functional area were answered, no score will be provided for that category (even if answers on aids or equipment are available).

HAQ-DI score is only calculated if there are at least 6 functional area scores available. The average of these non-missing functional area scores defines the continuous HAQ-DI score ranging from 0 to 3. If there are less than 6 functional area scores available, no imputation will be done, and the HAQ-DI will be set to missing for the corresponding assessment.

A HAQ-DI score reduction from baseline by 0.22 represents the MCID.

8.2.6 hsCRP

Blood concentration of hsCRP (mg/L) for all subjects will be determined by a central laboratory.

8.3 Primary Efficacy Endpoint

- ACR20 response at Week 12

8.3.1 Definition

A subject achieves ACR20 response when this subject experiences a $\geq 20\%$ improvement from baseline on the day of informed consent to Week 12 in TJC28, SJC28, and at least 3 of the following 5 items:

- Subject's pain assessment
- SGA
- EGA
- HAQ-DI
- hsCRP

For all visits, if any of the component scores are missing, then those scores will be considered as not having met the criteria for improvement. If 3 or more of the 5 remaining ACR measures are missing, ACR20 will each be considered as "no response" in the final dataset.

For component scores with missing baseline values or a baseline value of 0, the percentage improvement cannot be calculated, and the component will be considered as not having met the criteria for improvement for all visits.

8.3.2 Statistical Hypothesis

The hypothesis of interest is:

$$H_0: p_t - p_c = 0$$

$$H_1: p_t - p_c > 0$$

where p_t is the response rate in the treatment group and p_c is the response rate in the control group. The study will test the null hypothesis (H_0) that there is no difference between the treatment and control groups in the proportion of subjects achieving ACR20 response at Week 12 versus the alternative hypothesis (H_1) that treatment group response rate exceeds the control group response rate. The study will be considered successful if there is a statistically significant improvement in the proportion of subjects with ACR20 response in favor of the SetPoint System at the one-sided alpha of 0.025.

8.3.3 Primary Analysis

The primary analysis of the ITT population will be the CMH test. ACR20 response is the outcome variable. Subjects who received rescue treatment before Week 12 or who had missing data at Week 12 will be considered non-responders in the primary analysis.

8.3.4 Sensitivity Analyses

Sensitivity analysis for rescue intervention

Because rescue interventions can potentially confound the primary efficacy outcome, a sensitivity analysis will be performed to test the robustness of the efficacy conclusion to actual interventions given.

In this analysis, data imputations will be performed if intervention is given prior to Week 12, then ACR20 value prior to the intervention will be used in the analysis (LOCF).

Sensitivity analysis for missing data

Subjects with missed visit, lost to follow-up or partial ACR20 will be considered as missing data. If more than 5% of the primary efficacy data are missing, the following imputation analyses will be performed to assess the sensitivity of conclusions to missing data:

- A “tipping point” analysis in which all the primary analysis will be performed with all combinations of missing data. For instance, with M_c subjects with missing Week 12 data in the control group and M_t subjects with missing Week 12 data in the treatment group, then all $M_c \times M_t$ possible interims are completed. Between-treatment comparisons will be performed using a chi-squared test for each possible combinations of J (from 0 to M_c) and K (from 0 to M_t). The tipping point analysis will include the following cases:
 - Impute “ACR20 responder” for all missing values in the control group and “ACR20 non-responder” in the treatment group; this is a worst-case imputation.
 - Impute “ACR20 non-responder” for all missing values in the control group and “ACR20 responder” in the treatment group; this is a best-case imputation.

- If the decision about the null hypothesis using worst-case imputation agrees with the decision about the null hypothesis using best-case imputation, the tipping point analysis will include no further cases.
- In addition, an analysis will be conducted in which ACR20 responder or non-responder will be imputed based upon the last observed value (at Week 8 or Week 4) according to fully conditional specification predictive mean matching multiple imputation approach of Berglund and Heeringa (2014).

8.3.5 Subgroup Analyses

The primary efficacy endpoint will be examined using the following subgroups (including but not limited to the ones listed below):

- Age (< 65 vs. \geq 65)
- Gender (male vs. female)
- Race (White vs. Non-White, including Black or African American, American Indian or Alaska Native, Asian, Native Hawaiian or other Pacific Islander)
- Duration of RA (< 5 years vs. \geq 5 to < 10 years vs. \geq 10 years)
- Number of prior biologic and targeted synthetic DMARDs (e.g., < 4 vs. \geq 4)
- Prior use of JAKi (Yes vs. No)
- RA disease activity at Screening (DAS28-CRP \leq 5.1 vs. DAS28-CRP $>$ 5.1)
- Moderate-to-severe RA at Day 0 (< 4 TJC28 or < 4 SJC28 vs. \geq 4 TJC28 and \geq 4 SJC28)

8.4 Key Secondary Endpoints

- ACR20 response at Week 12 from Day 0
- DAS28-CRP good/moderate EULAR response at Week 12 from baseline
- DAS28-CRP response (MCID -1.2) at Week 12 from baseline
- HAQ-DI response (MCID -0.22) at Week 12 from baseline

8.4.1 Definitions of key secondary endpoints

ACR20 response at Week 12 from Day 0

A subject achieves ACR20 response when this subject experiences a \geq 20% improvement at Week 12 from the post-surgical baseline at Day 0 in TJC28 and SJC28 and 3 out of 5 ACR core measures and follows the same general and statistical analyses as for ACR20 response at Week 12 from baseline on the day of informed consent (see Section 8.3.1).

DAS28-CRP good/moderate EULAR response at Week 12

DAS28-CRP EULAR response at Week 12 is defined based on the combination of the current DAS28-CRP score and its improvement relative to baseline on the day of inform consent as illustrated in **Table 7**.

Table 7: EULAR Response Criteria

DAS28-CRP Score Week 12	DAS28-CRP Score Decrease from Baseline Value		
	> 1.2	> 0.6 to ≤ 1.2	≤ 0.6
≤ 3.2	Good response	Moderate response	No response
> 3.2 to ≤ 5.1	Moderate response	Moderate response	No response
> 5.1	Moderate response	No response	No response

A subject is considered having a moderate treatment response at Week 12 if:

- DAS28-CRP score improvement from baseline to Week 12 is > 0.6 and ≤ 1.2 , and the DAS28-CRP score at Week 12 is ≤ 5.1 ; or
- DAS28-CRP score improvement from baseline to Week 12 is > 1.2 , and the DAS28-CRP score at Week 12 is > 3.2 .

A subject is considered having a good treatment response at Week 12 if:

- DAS28-CRP score improvement from baseline to Week 12 is > 1.2 and the DAS28-CRP score at Week 12 is ≤ 3.2 .

If the post-baseline DAS28-CRP score is missing, then the corresponding EULAR category will be missing.

Missing DAS28-CRP values will be considered as not achieving remission.

DAS28-CRP response (MCID -1.2) at Week 12

A DAS28-CRP score reduction by at least 1.2 from baseline on the day of inform consent to Week 12 represents the MCID response (see Section 8.6.1).

HAQ-DI response (MCID -0.22) at Week 12

A HAQ-DI score reduction by at least 0.22 from baseline on the day of inform consent to Week 12 represents the MCID response (see Section 8.2.5).

8.5 Multiplicity Adjustment of Key Secondary Endpoints

This section describes the methods that will be used to control the familywise type 1 error rate (FWER) among these 4 secondary endpoints. If and only if the primary efficacy objective is met,

the Hochberg's step-up procedure (Hochberg 1988) will be used to control the FWER at a 1-sided significance level of 0.025 for the following 4 secondary endpoints:

ACR20 response at Week 12 from Day 0

- Test: $H_0: pt - pc = 0$ $H_1: pt - pc > 0$, using stratified CMH test, as detailed in Section 5.1

DAS28-CRP good/moderate EULAR response at Week 12 from baseline on the day of informed consent

- Test: $H_0: pt - pc = 0$ $H_1: pt - pc > 0$, using stratified CMH test

DAS28-CRP response (MCID -1.2) at Week 12 from baseline on the day of informed consent

- Test: $H_0: pt - pc = 0$ $H_1: pt - pc > 0$, using stratified CMH test

HAQ-DI response (MCID -0.22) at Week 12 from baseline on the day of informed consent

- Test: $H_0: pt - pc = 0$ $H_1: pt - pc > 0$, using stratified CMH test

The procedures rank the p-values from the above 4 tests from the least significant and examines the other p-values in a sequential manner until it reaches the most significant one, i.e., $p(4) > p(3) > p(2) > p(1)$.

The decision rule for the Hochberg procedure is defined as follows:

- Step 1. If $p(4) > 0.025$, retain $H(4)$ and go to the next step. Otherwise reject all hypotheses and stop.
- Step 2. If $p(3) > 0.025/2$, retain $H(3)$ and go to the next step. Otherwise reject all hypotheses and stop.
- Steps 3. If $p(2) > 0.025/3$, retain $H(2)$ and go to the next step. Otherwise reject all remaining hypotheses and stop.
- Steps 4. If $p(1) > 0.025/4$, retain $H(1)$ otherwise reject it.

The adjusted p-value is calculated as detailed below:

- Adjusted $p(i) = p(4)$ for $i = 4$ other adjusted $p(i) = \min [adjusted\ p(i+1), (5-i)*p(i)]$ for $i = 3, 2, 1$.

If any adjusted p-value exceeds 1, it is set to 1. Using this procedure, any adjusted p-value that is < 0.025 is statistically significant and supports a claim for the corresponding endpoint, while any adjusted p-value ≥ 0.025 is not statistically significant. Both adjusted and unadjusted p-values will be reported.

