17.4 Analysis of Key Secondary Endpoints

To support potential device labeling claims, a subset of secondary endpoints will be identified and analyzed using appropriate methods for controlling for family-wise type-1 error rate (FWER). This will be detailed in the SAP that will be submitted to the agency prior to the formal interim analysis.

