Repeat Table 14.1.2.1.5 for RA Disease Activity at Screening [DAS28-CRP \leq 5.1 vs DAS28-CRP $>$ 5.1]

Add to abbreviations: *DAS*, *Disease Activity Score*.

Table 14.1.2.1.11
 Subgroup Analysis of ACR20 Response: Moderate-to-severe RA at Day 0
 (ITT Population)

Variable	Treatment (N=xxx)	Control (N=xxx)
Moderate-to-severe RA at Day 0		
< 4 TJC28 or < 4 SJC28		
Week 12		
N [1]	xx	xx
Yes	xx (xx.x%)	xx (xx.x%)
Difference [2]	xx.x%	
95% CI for difference [2]	(xx.x, xx.x)	
p-value for difference [2]	0.xxx	
≥ 4 TJC28 and ≥ 4 SJC28		
Week 12		
N [1]	xx	xx
Yes	xx (xx.x%)	xx (xx.x%)
Difference [2]	xx.x%	
95% CI for difference [2]	(xx.x, xx.x)	
p-value for difference [2]	0.xxx	
Interaction p-value [3]	0.xxx	

Abbreviations: ACR, American College of Rheumatology; ITT, intent to treat.

[1] Percentage calculated based on ITT Population.

[2] Difference in proportions and one-sided p-value based on the Cochran-Mantel-Haenszel test stratified by inadequate response or loss of response to JAKi and RA disease severity at Day 0 for Stage 1 subjects and RA disease severity at Day 0 and inadequate response or loss of response to ≥ 4 biological DMARDs with ≥ 2 mechanisms of action for Stage 2 subjects.

[3] Based on the Breslow Day test for homogeneity across subgroups.

Reference: Listing 16.x.x.x

SOURCE: xxxxx SAS 9.4 {program location} {run date/time}}

Table 14.1.2.2
Key Secondary Endpoints Adjusted for Multiplicity
(ITT Population)

Endpoint	Unadjusted p-value	Adjusted p-value [1]
ACR20 response at Week 12 from baseline at Day 0	x.XXXX	x.XXXX
DAS28-CRP moderate/good EULAR response at Week 12 from baseline on the day of informed consent	x.XXXX	x.XXXX
DAS28-CRP response (MCID \geq -1.2) at Week 12 from baseline on the day of informed consent	x.XXXX	x.XXXX
HAQ-DI response (MCID \geq -0.22) at Week 12 from baseline on the day of informed consent	x.XXXX	x.XXXX

Abbreviations: CRP, C-reactive protein; DAS, Disease Activity Score; EULAR, European League Against Rheumatism; HAQ-DI, Health Assessment Questionnaire Disability Index; ITT, intent to treat; MCID, minimal clinically important difference.

[1] Adjusted for multiplicity using Hochberg's Step-Up Method

Reference: Listing 16.x.x.x

SOURCE: xxxx SAS 9.4 {program location} {run date/time}}

CONFIDENTIAL

57 of 158

May not be reproduced outside of SetPoint Medical without written permission from Document Control.

Table 14.1.2.2.1
Key Secondary Endpoints
(PTE Population)

Variable	Treatment (N=xxx)	Control (N=xxx)

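### SAP 8.5 gives two conflicting decision rules for the key secondary endpoints: Step 2 as written rejects the hypothesis that Step 1 has just retained, and the adjusted p-values do not

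*SAP*

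**What the plan says.** Protocol 17.4 gives the purpose of this family ("To support potential device labeling claims, a subset of secondary endpoints will be identified") and leaves the method to the SAP. SAP 8.5 says that, once the primary objective is met, "the Hochberg's step-up procedure (Hochberg 1988) will be used" and that it "will be used to control the FWER at a 1-sided significance level of 0.025" across four endpoints: ACR20 from Day 0, EULAR good/moderate response, DAS28-CRP MCID response and HAQ-DI MCID response. The p-values are ordered so that p(4) is the largest.

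Two rules follow in the same section.

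- **Step list**, introduced by "The decision rule for the Hochberg procedure is defined as follows". Step 1 retains H(4) and moves on if p(4) > 0.025, and otherwise rejects everything. Step 2 reads: "If $p(3) > 0.025/2$, retain $H(3)$ and go to the next step. Otherwise reject all hypotheses and stop". Step 3, at 0.025/3, ends differently: "Otherwise reject all remaining hypotheses and stop".
- **Adjusted p-values.** Adjusted p(4) equals p(4). For i = 3, 2, 1, adjusted p(i) is the smaller of adjusted p(i+1) and (5 − i) × p(i). An adjusted value below 0.025 "is statistically significant and supports a claim for the corresponding endpoint"; one at or above 0.025 is not significant.

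The reporting shell, Table 14.1.2.2 in Appendix B, shows unadjusted and adjusted p-values, with the footnote "Adjusted for multiplicity using Hochberg's Step-Up Method".

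**The concern.** Step 1 sends the analyst to Step 2 only when H(4) has been retained. If p(3) is then at or below 0.0125, Step 2 says to reject every hypothesis, and that set includes H(4). Step 3 limits the rejection to hypotheses not yet decided; Step 2 lacks that limit. Read literally, Step 2 puts no ceiling on p(4): the weakest endpoint would be declared positive even at p = 0.90, provided the other three reach 0.0125.

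This arises in a realistic outcome, with three endpoints clearly positive and one that misses, which is when a claim on the fourth would be contested. A confirmatory plan should return one verdict per endpoint. Here the same endpoint is rejected under one rule and not significant under the other, and no clause says which rule takes precedence.

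**Working it through.** **1. Where the rules conflict.** The inputs are all in SAP 8.5: familywise alpha 0.025 one-sided, four hypotheses, step thresholds 0.025, 0.0125, 0.00833 and 0.00625. The verdicts on H(4) differ when p(4) > 0.025 (Step 1 retains it) and p(3) ≤ 0.0125 (Step 2 rejects everything). The adjusted rule has adjusted p(4) = p(4) > 0.025, so H(4) is not significant.

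**2. Worked example.** Take p(1) = 0.004, p(2) = 0.008, p(3) = 0.012, p(4) = 0.20.

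- Steps: 0.20 > 0.025, so retain H(4). Then 0.012 ≤ 0.0125, so Step 2 rejects all four.
- Adjusted p(4) = 0.20.
- Adjusted p(3) = min(0.20, 2 × 0.012) = 0.024.
- Adjusted p(2) = min(0.024, 3 × 0.008) = 0.024.
- Adjusted p(1) = min(0.024, 4 × 0.004) = 0.016.
- Three values are below 0.025; the fourth is not.

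**3. The plan's own figure.** Simulation (400,000 draws per scenario, four one-sided normal tests, correlation 0, 0.5 or 0.8, effects scaled to 125 per arm) gives a familywise error of 0.017 to 0.025 under the adjusted p-value rule, for one to four true nulls. The stated 0.025 is therefore reproduced for that rule. Its formula also matched a standard software implementation of Hochberg on 5,000 random sets of p-values. With Step 2 limited to the remaining hypotheses, the step list and the adjusted rule agreed on all 100,000 random sets tried.

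**4. Size if Step 2 is followed literally (illustrative).** The documents give no effects or correlations for these endpoints. I assume 120 per arm (the 240 minimum in SAP 3.4), a 30% control rate as planned for the primary endpoint, and equal correlations. Each true effect has

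z = (p_t − p_c) / √{[p_t(1 − p_t) + p_c(1 − p_c)] / 120}.

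For 50% versus 30%, z = 0.20 / √(0.46/120) = 0.20 / 0.0619 = 3.23.

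With one true null, literal Step 2 rejects it whenever the other three are all ≤ 0.0125 (critical value 2.241). At zero correlation this gives a floor of Φ(z − 2.241)³:

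- 45%: Φ(0.189)³ = 0.575³ = 0.190
- 50%: Φ(0.989)³ = 0.839³ = 0.590
- 60%: Φ(2.659)³ = 0.996³ = 0.988

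Simulated familywise error, 400,000 draws per cell, correlation 0 / 0.3 / 0.7:

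| Other three endpoints | z | Literal Step 2 | Literal Step 2, after the primary gate |
|---|---|---|---|
| 45% vs 30% | 2.43 | 0.199 / 0.274 / 0.386 | 0.137 / 0.230 / 0.364 |
| 50% vs 30% | 3.23 | 0.598 / 0.640 / 0.714 | 0.536 / 0.599 / 0.699 |
| 60% vs 30% | 4.90 | 0.989 / 0.989 / 0.990 | 0.987 / 0.987 / 0.990 |

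The gate is a primary test with the same effect and correlation. Under the adjusted p-value rule the ungated scenarios give 0.015 to 0.025.

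**5. Where it does no harm.** With two or more true nulls, the conflict adds no familywise error. If p(3) ≤ 0.0125, at least one true null is already among the rejected H(1) to H(3). Simulated error was identical under both rules.

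**6. How often the rules would disagree.** If all four endpoints truly work, at 45% to 60% versus 30% with correlation 0.3 to 0.7, they disagree on H(4) in 0.3% to 18% of trials.

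**The case against.** The strongest reply is that the intended rule is plain. The section names Hochberg and promises familywise control. Step 1 has already retained H(4), and Step 3 has the right restriction. The adjusted p-value formula is standard Hochberg. The only sentence in 8.5 about claims rests on adjusted p-values, and Table 14.1.2.2 has no column for step-list decisions, so no planned output would change.

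The large error rates also need exactly one true null, three real effects and literal use of Step 2. The equal-correlation model ignores the overlap between endpoints: under SAP Table 7, any DAS28-CRP fall above 1.2 is at least a moderate EULAR response, so the MCID endpoint is nearly nested in the EULAR endpoint. A lone null in that pair is hard to construct; HAQ-DI or ACR20 from Day 0 is the more plausible candidate.

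Much of this stands. It is very probably a drafting slip, the intended analysis can be recovered, and the simulated rates only illustrate the literal reading. It does not remove the defect. The faulty sentence sits in the text the SAP itself labels the decision rule. The claim sentence favours the adjusted p-values but is not a precedence clause. A programmer or assessor working from the steps would reach a different verdict.

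**Conclusion.** The concern holds. SAP 8.5 contains two prespecified rules that give opposite verdicts on the weakest endpoint whenever p(4) > 0.025 and p(3) ≤ 0.0125. That conclusion follows from the text and needs no assumption. The familywise error rates for the literal reading (about 0.20 to 0.99 with one true null, ungated) depend on borrowed response rates, 120 per arm and assumed correlations. Because the adjusted p-value rule is correct and is the one linked to claims and reporting, error control is not lost if it is the rule used. The primary test, the gate, the sample size and the power are unaffected. The contradiction should be corrected, but it does not threaten the trial's main conclusion.

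**What to change.** In SAP 8.5, Step 2, limit the rejection to the hypotheses still undecided, H(3), H(2) and H(1), as Step 3 already does for its own level. Add a sentence that the adjusted p-values determine which endpoints support a claim.

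In the same edit, align the boundary. The steps reject when a p-value equals its threshold, whereas the adjusted rule needs a value strictly below 0.025. With p(4) exactly 0.025, for example, the steps reject all four and the adjusted rule does not support the fourth. This matters only for exact ties.

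The cost is a sentence or two in the SAP, best made before the primary dataset is locked and unblinded. Data, table shells and any program already using the adjusted p-values stay as they are.

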8.5.1 Sensitivity analyses of key secondary endpoints

The key secondary efficacy endpoints will be evaluated using the same sensitivity analyses for rescue intervention and missing data as those used for the primary efficacy endpoint (see Section

8.3.4). In addition, a sensitivity analysis for timing of baseline assessment will be performed to evaluate the impact of it on the secondary efficacy conclusions.

Sensitivity analysis for timing of baseline assessment

In this analysis, the baseline is defined as Day 0 assessments performed prior to randomization and initiation of stimulation.

